9.3 PK/PD Analysis

9.3.1 Pharmacokinetic (PK) Analysis

For subjects who agree to participate in the PK/PD substudy, PK samples will be drawn at Day 1 and Day 84 (Week 12) at predose, and 2, 6, and 8 hours postdose.

For subjects who are not in the PK/PD substudy, on Day 1 and Day 84 (Week 12), PK samples will be drawn on predose, between 1 to 3 hours postdose and then the last sample at least 1 hour after the second collection, for a total of 3 samples

For all subjects (including those in the PK/PD substudy), at visits on Week 2, 4, and 8, PK sampling will be collected predose, between 1 to 3 hours postdose and then the last sample at least 1 hour after the second collection, for a total of 3 samples at each visit.

9.3.1.1 PK/PD Substudy Analysis (Day 1 and Day 84)

For subjects who agree to participate in the PK/PD substudy, concentration data will be summarized by active treatment arm, visit and hours since last dose for post-baseline visits for EDP-305 and each metabolite. Concentrations that are below the limit of quantitation (BLQ) will be treated as zero for the computation of descriptive statistics. The number of observations, mean, standard deviation, % coefficient of variation, geometric mean, % geometric coefficient of variation, median, minimum, maximum values will be displayed. Figures will be created to display mean (+/- SD) and individual subject EDP-305 concentration time curves in plasma on both a linear and semi-logarithmic scale (for semi-logarithmic plots, no SD will be presented).

The PK parameters listed in Table 4 will be calculated as indicated for plasma EDP-305 and its metabolites, as applicable. PK parameters will be calculated by noncompartmental methods (AUC by linear up/log down method) (only on Day 1 and Day 84).

Plasma PK parameters for each dose level will be calculated from the concentrations of EDP-305 and its metabolites measured in predose and post-dose plasma samples. For each EDP-305 dose level, descriptive statistics (sample size, arithmetic means, geometric means, standard deviation (SD), % coefficient of variation (%CV), %GCV, minimum, median, and maximum) will be presented.

Individual data will be presented in listing.

Table 4: PK/PD Substudy Parameters

PK Parameter	Description
AUC_{last}	The area under the plasma concentration-time curve from time zero to the time of the last quantifiable concentration.
C_{max}	Maximum observed concentration.
T_{last}	Time to last quantifiable concentration.
T_{max}	Time to reach C _{max} . If the maximum value occurs at more than one timepoint, T _{max} is defined as the first time point with this value.

9.3.1.2 Population PK Analysis (Day 1 and Day 84)

For subjects not in the PK/PD substudy, the concentration data will be summarized by active treatment arm, visit and hours since last dose for EDP-305 and each metabolite. Concentrations that are below the limit of quantitation (BLQ) will be treated as zero for the computation of descriptive statistics. The number of observations, mean, SD, % CV, geometric mean, % GCV, median, minimum and maximum values will be displayed. Figures will be created to display mean and individual subject EDP-305 concentration time curves in plasma on both a linear and semi-logarithmic scale (for semi-logarithmic plots, no SD will be presented).

Individual data will be presented in listing.

9.3.1.3 PK Population Analysis

For Week 2, 4, and 8: For all subjects in the PK population (PK/PD substudy subjects and population PK subjects), the concentration data will be summarized by active treatment arm, visit and hours since last dose for post-baseline visits for EDP-305 and each metabolite for visits at Week 2, 4, and 8. Concentrations that are below the limit of quantitation (BLQ) will be treated as zero for the computation of descriptive statistics. The number of observations, mean, SD, % CV, geometric mean, % GCV, median, minimum, maximum values will be displayed. Figures will be created to display mean and individual subject EDP 305 concentration time curves in plasma on both a linear and semi-logarithmic scale (for semi-logarithmic plots, no SD will be presented).

For all visits: A summary plot of the means and standard deviations of the pre-dose concentrations at each visit (Day 1, Week 2, 4, 8, and 12) will be provided by treatment on both a linear and semi-logarithmic scale (for semi-logarithmic plots, no SD will be presented).

Individual data will be presented in listing.

9.3.2 Pharmacodynamic (PD) Analysis

The PD analysis will use the efficacy population and will include active treatment arms and placebo arms.

For subjects who agree to participate in the PK/PD substudy, PD samples (FGF19, C4, bile acids (BA), and ALP) will be drawn at Day 1 and Day 84 (Week 12) at predose, 2, 6, and 8 hours postdose. At visits on Week 2, 4, and 8, PD sampling will be collected predose, between 1 to 3 hours postdose and then the last sample at least 1 hour after the second collection, for a total of 3 samples at each visit.

For subjects who are not in the PK/PD substudy, PD samples (FGF19, C4, bile acids (BA)) will be drawn predose.

9.3.2.1 PD Substudy Analysis (Day 1 and Day 84)

9.3.2.1.1 FGF19

A descriptive summary will be provided for the PD parameters such as AUC_{0-8} and AUC_{2-8} for FGF19 at Day 1 and Day 84 (Week 12), change from Baseline in the AUC values at Week 12 and percentage change from baseline in the AUC values at Week 12 using 8-number summary by visit and treatment group.

Change from Baseline and the percentage change from baseline in the AUC_{0-8} and the AUC_{2-8} for FGF19 at Week 12, will be analyzed using an ANCOVA model with treatment as fixed effect and the associated baseline value as covariate. Least squares means and standard errors will be presented for each visit, p-value and 2-sided 95% confidence interval for treatment differences will be presented for each visit. Significance tests will be based on least-squares means using a two-sided $\alpha = 0.05$.

The above analysis will be repeated for the actual FGF19 values (concentrations), the change from Baseline and the percentage change from Baseline values at time point and each visit for the PD substudy subjects.

Individual Plasma Concentrations as well as Mean \pm SD and change from baseline for FGF19 values by visit and treatment group will be plotted.

A by-subject listing will be provided for observed and derived variables.

9.3.2.1.2 C4

A descriptive summary will be provided for the PD parameters such as AUC_{0-8} and AUC_{2-8} for C4 at Day 1 and Day 84 (Week 12), change from Baseline in AUC at Week 12 and percentage change from baseline in the AUC at Week 12 values using 8-number summary by visit and treatment group.

Change from Baseline and the percentage change from baseline in the AUC₀₋₈ and the AUC₂₋₈ for C4 at Week 12, will be analyzed using an ANCOVA model with treatment as fixed effect and the associated baseline value as covariate. Least squares means and standard errors will be presented for each visit, p-value and 2-sided 95% confidence interval for treatment differences will be presented for each visit. Significance tests will be based on least-squares means using a two-sided $\alpha = 0.05$.

The above analysis will be repeated for the actual C4 values (concentrations), the change from Baseline and the percentage change from Baseline values at time point and each visit for the PD substudy subjects.

Individual Plasma Concentrations as well as Mean \pm SD and change from baseline for C4 values by visit and treatment group will be plotted.

A by-subject listing will be provided for observed and derived variables.

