6.2 Baseline

For the primary endpoint, baseline will be defined in 3 ways: 1.) the average between the screening and the day 1 visits. If either is missing, the non-missing value will be considered baseline for this approach. This is the primary definition for the study 2.) The Day 1 value or the last value prior to first dose of study drug. 3.) The value from the screening visit as the baseline. The primary endpoint will be evaluated using all 3 baseline calculations. For all secondary and safety endpoints, baseline will be defined using method 2.) above.

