6.3 Study Day Windows

The windows for all visits including PK draws appear in table below:

Visit	Target Day	Time window
Screening	Day -1	Day -28 to Day -1
Day 1	Day 1	N/A
Day 3	Day 3	N/A
Week 2	Day 14	Day 4 to Day 21
Week 4	Day 28	Day 22 to Day 42
Week 8	Day 56	Day 43 to Day 70
Week 12	Day 84	Day 71 to less than or equal to End of Treatment+7 days
Treatment-Free Follow-up Week 4	Day 112	Greater than End of Treatment+7 days to last visit

- Samples at each visit should be obtained at different times postdose relative to each of the other visits (2, 4, and 8)
- The target day for the screening visit is Day -1 during the period of Day -28 to Day -1

The relative day will be computed for each laboratory, vitals, ECG and PD data point. The relative day will be calculated as visit date-date of first dose+1. For data collected prior to first dose, the relative day will be calculated as visit date-date of first dose. When there are multiple observations within a visit window, the value closest to the target day will be analyzed..

PK/PD Draw Timing

Visit	Target Day	PK/PD Substudy (PK, C4, FGF19, BA, and additional ALP samples)	Population	
			For subjects not substudy	
			PK	PD (FGF19, BA, C4)
Day 1	Day 1	At predose and 2, 6, and 8 hr postdose	at predose and two samples postdose; 
 • First sample collected 1 to 3 hours postdose • Second sample at least 1 hour later 	At predose
Week 2	Day 14	at predose and two samples postdose; 
 • First sample collected 1 to 3 hours postdose • Second sample at least 1 hour later 	at predose and two samples postdose; 
 • First sample collected 1 to 3 hours postdose • Second sample at least 1 hour later 	At predose
Week 4	Day 28	at predose and two samples postdose; 
 • First sample collected 1 to 3 hours postdose • Second sample at least 1 hour later 	at predose and two samples postdose; 
 • First sample collected 1 to 3 hours postdose • Second sample at least 1 hour later 	At predose
Week 8	Day 56	at predose and two samples postdose; 
 • First sample collected 1 to 3 hours postdose • Second sample at least 1 hour later 	at predose and two samples postdose; 
 • First sample collected 1 to 3 hours postdose • Second sample at least 1 hour later 	At predose

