9.3.2.1.3 Bile Acid

A descriptive summary will be provided for the bile acid concentrations, change from Baseline and the percentage change from baseline using 8-number summary by visit and treatment group.

Change from Baseline and the percentage change from baseline in the bile acid for each time point by visit, with the Week 12 visit being considered the primary visit of interest, will be analyzed using an ANCOVA model with treatment as fixed effect and the associated baseline value as covariate. Least squares means and standard errors will be presented for each visit, p-value and 2-sided 95% confidence interval for treatment differences will be presented for each visit. Significance tests will be based on least-squares means using a two-sided $\alpha = 0.05$.

Individual Plasma Concentrations as well as Mean \pm SD and change from baseline for Bile Acid values by visit and treatment group will be plotted.

A by-subject listing will be provided for observed and derived variables.

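### The FGF19 and C4 AUC change analyses have no pre-treatment baseline: the only AUC before Week 12 is the Day 1 profile, which is mostly or wholly after the first dose

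*SAP*

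**What the plan says.** SAP 9.3.2 sets the substudy sampling: FGF19, C4, bile acid and ALP "will be drawn at Day 1 and Day 84 (Week 12) at predose, 2, 6, and 8 hours postdose". At Weeks 2, 4 and 8 there are three samples with flexible postdose times, and no AUC is planned.

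SAP 9.3.2.1.1 (FGF19) and 9.3.2.1.2 (C4) summarise AUC0-8 and AUC2-8 at Day 1 and Day 84, and then "change from Baseline in the AUC values at Week 12 and percentage change from baseline in the AUC values at Week 12". Change and percent change in these AUCs "will be analyzed using an ANCOVA model with treatment as fixed effect and the associated baseline value as covariate", with p-values and 95% confidence intervals. Neither section says which AUC is the baseline.

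The general rule is in SAP 6.2. Method 2 is "The Day 1 value or the last value prior to first dose of study drug", and "For all secondary and safety endpoints, baseline will be defined using method 2.) above". The PD markers are secondary endpoints (protocol 2.2.2), so method 2 applies. Protocol 7.1.3 treats the predose Day 1 assessments as Baseline; the first dose and then the biomarker draws follow. The schedule of assessments has no FGF19, C4 or bile acid sample at Screening.

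**The concern.** Method 2 is clear for a single concentration: the predose Day 1 sample meets both halves of it. It does not work for an AUC. No AUC exists before the first dose, so only the words about the Day 1 value are left, and the Day 1 AUC is built mainly from samples taken after dosing. That conflicts with the protocol's meaning of Baseline.

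In the active arms, treatment could then alter both the quantity subtracted and the covariate. Placebo is not affected in this way, so randomisation does not cancel the distortion. What is at stake is the estimated size of the FGF19 and C4 AUC effect and its confidence interval. Ten plots in SAP 9.3.3.1 also use percent change in these AUCs: four against EDP-305 AUClast, four against ALT, and two C4 box plots by pruritus status.

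**Working it through.** The documents give no power or expected value for the AUC change, so there is no planned figure to reproduce. The check has three steps.

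**1. How much of the Day 1 AUC is post-dose.** Inputs: sampling at 0, 2, 6 and 8 h (SAP 9.3.2). Linear trapezoid:

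- AUC0-8 = 1(C0+C2) + 2(C2+C6) + 1(C6+C8) = C0 + 3·C2 + 3·C6 + C8. Weights are 1/8, 3/8, 3/8, 1/8, so 7/8 = 87.5% is post-dose.
- AUC2-8 = 2(C2+C6) + 1(C6+C8) = 2·C2 + 3·C6 + C8. All of it is post-dose.

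**2. Raw change.** Let e be the steady-state effect and f the share of it already present at 2 to 8 h on Day 1. Assumptions: a flat untreated level, and the protocol 4.2.2 maximal C4 falls of about 67% and 85% taken as AUC effects. As a fraction of the untreated AUC, the change seen in AUC2-8 is e(1−f) instead of e. The percent change seen is:

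- AUC2-8: (1+e)/(1+f·e) − 1
- AUC0-8: (1+e)/(1+0.875·f·e) − 1

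Example, e = −0.67, f = 0.50, AUC2-8: 0.33/0.665 − 1 = −50.4%.

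| f | AUC2-8, true −67% | AUC2-8, true −85% | AUC0-8, true −67% | AUC0-8, true −85% |
|---|---|---|---|---|
| 0 | −67.0% | −85.0% | −67.0% | −85.0% |
| 0.25 | −60.4% | −81.0% | −61.3% | −81.6% |
| 0.50 | −50.4% | −73.9% | −53.3% | −76.1% |
| 1 | 0.0% | 0.0% | −20.2% | −41.5% |

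**3. The planned ANCOVA of change.** With Day 1 AUC as covariate, the treatment contrast in change equals that of Week 12 AUC adjusted for Day 1 AUC. It is τ − b·(f·τ) = τ(1 − b·f), where τ is the true Week 12 contrast and b the slope of Week 12 on Day 1 AUC.

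Simulation for C4 AUC2-8: 20,000 trials per setting and three arms of 10, the substudy minimum in SAP section 5. Assumed: lognormal values with untreated mean 100 and CV 60%, log-scale correlation 0.5 or 0.7 between predose, Day 1 and Week 12, and the same f in both doses.

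| Arm, correlation | f = 0 | f = 0.25 | f = 0.50 |
|---|---|---|---|
| −67%, 0.5 | −66.2 | −61.4 | −54.9 |
| −67%, 0.7 | −66.0 | −59.0 | −49.9 |
| −85%, 0.5 | −84.0 | −78.0 | −69.7 |
| −85%, 0.7 | −83.7 | −75.0 | −63.3 |

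Examples of understatement relative to f = 0: 1 − 61.4/66.2 = 7% and 1 − 59.0/66.0 = 11% at f = 0.25; 1 − 54.9/66.2 = 17% and 1 − 49.9/66.0 = 24% at f = 0.50. Repeat runs move these by a few tenths of a point, so the range at f = 0.50 is about 17-25%. At f = 1 it is about 47-69%.

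Rejection in the −67% arm at f = 0 / 0.25 / 0.50 is 99.4 / 98.4 / 94.6% (correlation 0.5) and 99.8 / 99.4 / 95.8% (0.7). At f = 1 it falls to about 51% and about 34-35%.

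The percent-change ANCOVA behaves differently. With correlation 0.5 at f = 0 it already gives −78.5 and −99.6 for true −67 and −85, because it is a ratio to a noisy baseline. At f = 0.50 it gives −72.6 and −103.8, so the two arms move in opposite directions.

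**Check of the alternative.** An ANCOVA of Week 12 AUC on the Day 1 predose value, under the same assumptions, stays at about −66 and −84 at every f.

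No FGF19 size is given: for a rise of the order in protocol 4.2.2, the ratio to a Day 1 AUC depends almost wholly on the assumed f.

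**The case against.** **A baseline rule exists.** SAP 6.2 covers secondary endpoints, and 9.3.2.1 names Day 1 and Day 84 as the AUC days, so a reader could see what is compared. That is fair: the SAP is not silent on baseline. But the rule has no pre-treatment AUC to select, and being able to see that Day 1 is used does not make it pre-treatment.

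**The size is not in the documents.** This stands. The value of f is not in the readable text, parts of the Phase 1 and dose-rationale sections are redacted, and the CV, correlations and equal f are assumptions.

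**The scope is small.** This also stands. It is a substudy analysis, the protocol endpoint does not name AUC change, and Day 1 and Week 12 AUCs are shown by arm.

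A reader might infer that the by-time-point analyses of FGF19 and C4 ("the change from Baseline and the percentage change from Baseline values at time point and each visit for the PD substudy subjects") and bile acid ("Change from Baseline and the percentage change from baseline in the bile acid for each time point by visit") share the defect, through a time-matched Day 1 baseline. The documents do not support that. For a concentration, method 2 read with protocol 7.1.3 gives the predose value, and no section mentions a time-matched baseline.

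A reader might also take SAP 9.3.3.1 as proof that Baseline means the Day 1 profile, because one plot there uses percent change from Baseline in drug AUClast. That is one item; the other AUClast scatterplots use AUClast itself. It may be a drafting slip and is only weak support.

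**Conclusion.** The concern holds for the FGF19 and C4 AUC change analyses and the ten percent-change AUC plots in SAP 9.3.3.1. The only baseline AUC available is 87.5% or 100% post-dose by weight, so it is not pre-treatment. Attenuation is conditional: it arises if the first dose moves the marker within 8 hours in the steady-state direction, and there is none at f = 0. It applies to raw change, raw percent change and the ANCOVA of change. No direction is claimed for the percent-change ANCOVA.

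Under the stated C4 assumptions the change-ANCOVA contrast is understated by about 7-11% at f = 0.25, 17-25% at f = 0.50 and 47-69% at f = 1. Up to f = 0.50 the harm is to effect size, with rejection still about 95% or more. It would be wrong to conclude either that detection is always safe or that the tests will fail: power drops sharply only as f nears 1, and f is unknown.

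The primary ALP endpoint and the predose PD analyses are unaffected. This should be corrected, but it does not threaten the trial's main conclusion.

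**What to change.** In SAP 9.3.2.1.1 and 9.3.2.1.2:

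- Make the Week 12 inference an ANCOVA of Week 12 AUC0-8 and AUC2-8, each dose against placebo, with the Day 1 predose concentration as covariate. A log scale is optional; the check above used the raw scale.
- Report Day 1 AUC by arm as a separate first-dose outcome.
- Label any Day 1 to Week 12 AUC contrast that is kept, and the ten plots in 9.3.3.1, as *change from first-dose (Day 1) profile*.

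For the by-time-point concentration analyses in 9.3.2.1.1 to 9.3.2.1.3, add one sentence confirming that baseline is the Day 1 predose value under SAP 6.2 method 2. This is a clarification, not the repair of a defect.

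The cost is SAP wording and programming, with no new samples. The downside is that a single predose value is a noisier covariate than a full profile. The placebo comparison handles the time-of-day pattern in the ANCOVA, but the plots against EDP-305 AUClast contain only treated subjects and will still carry it.

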9.3.2.1.3 Bile Acid

A descriptive summary will be provided for the bile acid concentrations, change from Baseline and the percentage change from baseline using 8-number summary by visit and treatment group.

Change from Baseline and the percentage change from baseline in the bile acid for each time point by visit, with the Week 12 visit being considered the primary visit of interest, will be analyzed using an ANCOVA model with treatment as fixed effect and the associated baseline value as covariate. Least squares means and standard errors will be presented for each visit, p-value and 2-sided 95% confidence interval for treatment differences will be presented for each visit. Significance tests will be based on least-squares means using a two-sided $\alpha = 0.05$.

Individual Plasma Concentrations as well as Mean \pm SD and change from baseline for Bile Acid values by visit and treatment group will be plotted.

A by-subject listing will be provided for observed and derived variables.

9.3.2.2 Population PD Analysis (Day 1 and Day 84)

9.3.2.2.1 FGF19

A descriptive summary will be provided for FGF19 concentrations, change from Baseline and the percentage change from baseline using 8-number summary by visit and treatment group.

Change from Baseline and the percentage change from baseline in the FGF19 for each time point by visit, with the week 12 visit being considered the primary visit of interest, will be analyzed using an ANCOVA model with treatment as fixed effect and the associated baseline value as covariate. Least squares means and standard errors will be presented for each visit, p-value and 2-sided 95% confidence interval for treatment differences will be presented for each visit. Significance tests will be based on least-squares means using a two-sided $\alpha = 0.05$.

Mean \pm SD and change from baseline for FGF19 values by visit and treatment group will be plotted.

A by-subject listing will be provided for observed and derived variables.

9.3.2.2.2 C4

A descriptive summary will be provided for C4 concentrations, change from Baseline and the percentage change from baseline using 8-number summary by visit and treatment group.

Change from Baseline and the percentage change from baseline in the C4 for each time point by visit, with the week 12 visit being considered the primary visit of interest, will be analyzed using an ANCOVA model with treatment as fixed effect and the associated baseline value as covariate. Least squares means and standard errors will be presented for each visit, p-value and 2-sided 95% confidence interval for treatment differences will be presented for each visit. Significance tests will be based on least-squares means using a two-sided $\alpha = 0.05$.

Mean \pm SD and change from baseline for C4 values by visit and treatment group will be plotted.

A by-subject listing will be provided for observed and derived variables.

9.3.2.2.3 Bile Acid

A descriptive summary will be provided for bile acid concentrations, change from Baseline and the percentage change from baseline using 8-number summary by visit and treatment group.

Change from Baseline and the percentage change from baseline in the bile acid for each time point by visit, with the week 12 visit being considered the primary visit of interest, will be analyzed using an ANCOVA model with treatment as fixed effect and the associated baseline value as covariate. Least squares means and standard errors will be presented for each visit, p-value and 2-sided 95% confidence interval for treatment differences will be presented for each visit. Significance tests will be based on least-squares means using a two-sided $\alpha = 0.05$.

Mean \pm SD and change from baseline for Bile Acid values by visit and treatment group will be plotted.

A by-subject listing will be provided for observed and derived variables.

